9 STUDY OVERSIGHT

In addition to the GPI's and Study Principal Investigator's (SPI) responsibility for oversight, study oversight will be under the direction of a Data and Safety Monitoring Board (DSMB) composed of members with expertise in dentistry, practice-based research, study design and statistics. The DSMB will meet at least annually to assess safety and efficacy data for the study. If safety concerns arise, more frequent meetings may be held. The DSMB will operate under the rules of an NIDCR-approved charter that will be approved at the organizational meeting of the DSMB. At this time, most data elements that the DSMB needs to assess will be clearly defined. The DSMB will provide recommendations to the NIDCR.

10 CLINICAL SITE MONITORING

Clinical site monitoring is conducted to ensure that the rights of human subjects are protected, that the study is implemented in accordance with the protocol and/or other operating procedures, and that the quality and integrity of study data and data collection methods are maintained. The network RAS will be responsible for clinical site monitoring for this study. RCs at each RAS will provide study training to practitioner sites and perform clinical site monitoring activities, to evaluate study processes and documentation based on NIDCR standards and principles of Good Clinical Practice guidelines. Clinical site monitoring will not occur for the pre and post study vignette data collection study since the CC is responsible for launching the vignettes and collecting data received as part of the vignette.

All details about clinical site monitoring will be documented in a Clinical Monitoring Plan (CMP) developed by Westat, under the direction of the National Dental PBRN, in collaboration with the NIDCR Office of Clinical Trials Operations and Management (OCTOM) and the NIDCR Program Official. The CMP will specify site training activities, the type and frequency of monitoring, monitoring procedures, the level of clinical site monitoring activities (e.g., the percentage of subject data to be reviewed), and the distribution of monitoring reports. Some monitoring activities may be performed remotely, while others will take place at each practitioner site. The RCs will provide reports of the findings from monitoring and associated action items in accordance with the details described in the CMP. Documentation of monitoring activities and findings will be provided to the practitioner, GPI, SPI, OCTOM, and NIDCR. NIDCR reserves the right to conduct independent audits as necessary.

11 STATISTICAL CONSIDERATIONS

11.1 Study Hypotheses

The primary objective of the study is to quantify the difference in proportions of SOCL that are treated operatively among the study groups. The null hypothesis for this objective is that the proportions of SOCL that are treated operatively are not different among the three study groups. The corresponding alternative hypothesis is that the proportion of SOCL treated operatively differs among the groups. The main interest is in comparing the proportions of SOCL treated operatively between each of the device groups and the no-device group. The null hypothesis that will be tested for each of these comparisons is that the proportions of SOCL treated operatively does not differ between the groups versus the alternative hypothesis that the proportions differ. The study will also quantify the differences in proportions of SOCL that extend into dentin, among those that are treated operatively in each study group. The null hypothesis is that there is no difference among the groups in the proportion of operatively treated SOCL that extend into dentin. The alternative hypothesis is that the proportions of operatively treated SOCL that extend into dentin differ among the groups. Here again, there is particular interest in the two pre-planned comparisons between each of the device groups and the no-device group. The null hypothesis for each of these comparisons is that there is no difference in the proportions of SOCLs that extend into dentin between the device and no-device groups, and the alternative hypothesis is that there is a difference in the proportions.

A secondary objective of the study is to identify clinical characteristics of operatively-treated SOCLs that predict caries extending into dentin. For each of the clinical characteristics that is considered, the null hypothesis is that there is no association with extension into dentin and the alternative hypothesis is that there is an association with extension into dentin. Practically, the goal will be to identify a multivariable statistical model that is predictive of caries extending into dentin. In addition to separate tests for each characteristic, the null hypothesis for the predictive model is that the set of clinical characteristics included in the model jointly have no association with caries extension into dentin. The alternative hypothesis is that a joint association is present.

11.2 Sample Size Considerations

Power to detect differences between each of the device groups and the no-device group was approximated based on two-sided testing with the Chi-square statistic, with adjustments for multiple comparisons and for the effect of clustering within practitioner. A Bonferroni-type adjustment was used to account for two comparisons: no device versus each of the device groups. This approach yields somewhat conservative estimates of power, since the two device-versus-control comparisons are pre-planned, and will each be conducted at the 95% confidence level in the statistical analysis of the actual study data, as described in the following section.

The unit of randomization is the individual practitioner. The effect of cluster randomization was taken into account in the calculation of study power and sample size requirements by adjusting the total sample size using the design effect, calculated as $1 + (m - 1)\rho$, where m = the average number of lesions per practitioner and $\rho =$ the intraclass correlation coefficient (ICC). The effective sample size was calculated by dividing the total sample size by the design effect. The effective sample size is the number of observations which would be required to achieve the same power, using an independently-randomized design, as the cluster-randomized design with the given total sample size. Power and detectable difference estimates were then calculated for the chi-square statistic using the effective sample sizes for values of ICC from 0.0 to 0.05.

Two outcomes are of interest: the proportion of all SOCL that are opened and the proportion of opened SOCL that are carious. Practitioners will each contribute 20 lesions to the study during the intervention period. The planned recruitment of 30 practitioners per group yields a total sample size of 600 lesions per group for the first outcome. The total sample size for the second outcome will be the number of lesions that are opened. Because the study design does not include follow-up of individual patients, patient-level dropout is not anticipated to be a major consideration. Drop-out of practitioners is possible, and could cause the loss of multiple observations, depending on the number of patients that are accrued prior to the practitioner drop-out, up to a maximum of 30. Part of the intent of the pre-intervention run-in period is to identify practitioners who are not likely to succeed in recruiting the required number of patients, and to provide an opportunity for practitioners to drop out prior to randomization, so that they can be replaced without interference to the randomization process. Still, it is possible that practitioners might drop out after randomization. Anticipating a severe situation in which 10% of the initial 30 practitioners in each group drop out prior to contributing any data, power and detectable difference calculations were repeated for 27 practitioners per group, and a total sample size of 540 lesions per group. While this is an extreme and unlikely occurrence, the additional tables provide an indication of the effect of a substantial loss of data.

The expected rates of lesion opening are 50% for no device and 30-35% for the device groups. Differences in rates of opening that would be detectable with 80% power are as follows:

Difference detectable with 80% power				ICC		
	0.00	0.01	0.02	0.03	0.04	0.05
Effective						
sample/group:	600	504	435	382	341	308
Detectable difference						
(%):	9.1	9.9	10.7	11.4	12.0	12.7
Rate in device group						
(%):	40.8	40.1	39.3	38.6	38.0	37.3

Assuming loss of 10% of practitioners per group, without contributing any data to the study:

Difference detectable with 80% power	ICC							
	0 0.01 0.02 0.03 0.04 0.0							
Effective comple/groups	E 40	454	204	244	207	077		
Effective sample/group:	540	454	391	344	307	211		
Detectable difference (%):	9.6	10.4	11.3	12.0	12.7	13.4		
Rate in device group (%):	40.4	39.6	38.7	38.0	37.3	36.6		

The proposed sample size would provide approximately 92% power to detect a difference in rates of opening of lesions, assuming the most restrictive set of conditions considered (rates of 50% vs 35%, ICC = 0.05). Power remains above 80% even if 10% of practitioners contribute no data. This provides some assurance that adequate power would be available, even if a somewhat smaller difference and/or somewhat larger value of ICC is observed.

The sample size for comparison of rates of caries into dentin among opened lesions will depend on the numbers of lesions that the dentists choose to open, and this will likely differ among groups. Assuming that 30 practitioners are recruited per group, each contributing 20 lesions, that 50% of lesions in the no-device group and 35% of lesions in the device groups will be opened, then the sample sizes for this question will be 300 lesions for the no-device group and 210 lesions in the device group. Assuming that 50% of opened lesions in the no-device group will be carious, the following table presents power to detect a difference between groups for percentages of 60%, 65%, 70% and 75% of opened lesions in the device group being carious.

	ICC							
	0.00	0.01	0.02	0.03	0.04	0.05		
% caries in device group	Power (%)							
65%	87	80	73	67	61	56		
70%	99	97	95	92	88	84		
75%	99	99	99	99	98	97		

Assuming loss of 10% of practitioners per group, without contributing any data to the study:

	ICC							
	0.00	0.01	0.02	0.03	0.04	0.05		
% caries in device group		Power (%)						
0.65	83	75	68	62	56	51		
0.7	98	95	92	88	84	80		
0.75	99	99	99	98	97	95		

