To determine whether the principal factors used by participating practitioners in managing SOCLs change when a caries detection device is employed, the Lens model analytic approach will allow for the determination of the unique contribution of each of the 4 principal features (color, luster, roughness, risk) to the treatment decision. An overall significance of each equation and the variance it accounted for will be determined for the decision to surgically intervene and the confidence of that decision. These represent the main a priori hypotheses from the decision study (vignette) portion of the project. In addition to those a priori hypothesized analyses, a number of more exploratory analyses are possible within the Lens model approach. This could include demographic characteristics of the dentists (age race, sex, experience in practice etc.). These individual difference variables would be included in the nomothetic analyses only. Finally, the similarity of treatment predictors will be examined across the in vivo and vignette portions of the study as an initial cross validation of the two approaches. We will examine the concordance rates and/or correlations between number of decisions to intervene across the two portions of the study and across groups (device trained vs. no device).

The proposed sample size, developed in the previous section was developed using conservative assumptions regarding effect size and potentially missing data. The study is anticipated to provide adequate statistical power even if approximately 20% of observations have missing values for some variables, depending on the differences and level of ICC that are actually observed in the study. Issues regarding missing values are presented in further detail in the Appendix E.

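### The power tables for the dentin outcome keep a design effect for 20 lesions per practitioner although only 10 or 7 are analysed, so they understate power, and the announced 60% row is missing

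*Protocol*

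**What the plan says.** Protocol section 3.2.1 lists extension into dentin, among surgically treated lesions, as the second of two primary outcomes.

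Section 11.2 sets out the power method:
- The basis is "two-sided testing with the Chi-square statistic".
- On multiplicity: "A Bonferroni-type adjustment was used to account for two comparisons: no device versus each of the device groups".
- The design effect is 1 + (m − 1) × ICC, where "m = the average number of lesions per practitioner".
- "The effective sample size was calculated by dividing the total sample size by the design effect", and power was then obtained "using the effective sample sizes for values of ICC from 0.0 to 0.05".

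For the dentin outcome, the section assumes 30 practitioners per group with 20 lesions each, and opening rates of 50% without a device and 35% with one. Hence "the sample sizes for this question will be 300 lesions for the no-device group and 210 lesions in the device group". The dentin rate without a device is taken as 50%. It then states that "the following table presents power to detect a difference between groups for percentages of 60%, 65%, 70% and 75" per cent. Both tables that follow (30 practitioners per group, and after 10% practitioner loss) have rows for 65%, 70% and 75% only. The value of m behind these two tables is not given.

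Section 11.3 adds: "The study is anticipated to provide adequate statistical power even if approximately 20% of observations have missing values for some variables". That sentence goes on to make the claim conditional on the differences and ICC actually observed. Appendix E repeats the claim with the same condition.

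**The concern.** The sample for this outcome is reduced to opened lesions, so the number of analysed lesions per practitioner falls too. The design effect has to fall with it. If the total is cut to 300 and 210 while m stays at 20, the calculation charges for correlation with lesions that are not in the analysis. The stated power of a primary outcome is then wrong.

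The missing 60% row matters for a different reason. It is the scenario with the lowest power of the four announced. Without it, the tables show no row for a 10-point difference, and a reader cannot see how the design performs there.

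**Working it through.** **Inputs (Protocol section 11.2).** Two-sided alpha 0.05/2 = 0.025 per comparison. Dentin rate p1 = 0.50 without a device; p2 = 0.60, 0.65, 0.70 or 0.75 with one. Lesions N1 = 300 and N2 = 210 from 30 practitioners per group. With 27 per group, N1 = 270 and N2 = 189.

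**Formulas.** DE = 1 + (m − 1) × ICC and n = N/DE in each arm. Power ≈ Φ[(|p1 − p2| − z × s0)/s1], where z = 2.2414, s0 is the pooled standard error √[p̄(1 − p̄)(1/n1 + 1/n2)], and s1 is the unpooled standard error √[p1(1 − p1)/n1 + p2(1 − p2)/n2]. No continuity correction.

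**Step 1: reproduce the printed figures.** Take 65% at ICC 0.05 with m = 20 in both arms.
- DE = 1 + 19 × 0.05 = 1.95, so n1 = 300/1.95 = 153.8 and n2 = 210/1.95 = 107.7.
- s0 = 0.0623 and s1 = 0.0611.
- (0.15 − 2.2414 × 0.0623)/0.0611 = 0.168, so power is 56.7%. The table prints 56.

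The whole 65% row at m = 20 is 87.3, 80.4, 73.6, 67.3, 61.7, 56.7, against printed 87, 80, 73, 67, 61, 56. All 36 cells in the two tables agree with m = 20 within 1 point. With m = 10/7, 8.5 or 10, under the other alpha and variance variants tried (alpha 0.05, unpooled variance, continuity correction), the largest deviation is between 11 and 28 points.

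**Step 2: apply the protocol's own m.** 300/30 = 10 and 210/30 = 7. The loss scenario gives the same values (270/27 = 10, 189/27 = 7). For 65% at ICC 0.05:
- DE = 1 + 9 × 0.05 = 1.45 and 1 + 6 × 0.05 = 1.30, so n1 = 206.9 and n2 = 161.5.
- s0 = 0.0520 and s1 = 0.0512.
- (0.15 − 2.2414 × 0.0520)/0.0512 ≈ 0.652, so power is 74.3%.

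Power (%) at alpha 0.025, for ICC 0.00 / 0.01 / 0.02 / 0.03 / 0.04 / 0.05:

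| Device rate | Practitioners per group | Printed | With m = 10 and 7 |
|---|---|---|---|
| 60% | 30 | no row | 50/47/44/41/39/37 |
| 65% | 30 | 87/80/73/67/61/56 | 87/85/82/79/77/74 |
| 70% | 30 | 99/97/95/92/88/84 | 99/99/98/97/96/95 |
| 60% | 27 | no row | 45/42/40/37/35/33 |
| 65% | 27 | 83/75/68/62/56/51 | 83/80/77/75/72/69 |
| 70% | 27 | 98/95/92/88/84/80 | 98/98/97/96/94/93 |

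The 75% row is above 99% throughout in both scenarios. The largest gap is 74 − 56 = 18 points with 30 practitioners and 69 − 51 = 18 with 27.

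**Step 3: the alpha planned for the analysis.** Section 11.2 and Appendix E say each comparison will be tested at the 95% level. At alpha 0.05 with m = 10/7 and 30 practitioners per group, the 60% row is 61/58/55/53/50/48. The 65% row runs from 92 down to 83.

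**Step 4: 20% missing.** N = 0.8 × 300 = 240 and 0.8 × 210 = 168; m = 8 and 5.6. At alpha 0.025, 65% gives about 78 down to 66, 70% gives 97 down to 91, and 75% stays above 99. At alpha 0.05, 65% gives about 86 down to 76.

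**The case against.** The strongest defence is that the error is on the safe side. A larger m overstates clustering, so true power is higher than printed. Section 11.2 sets no sample size from these tables, and it does not say which m they use, so 20 could be a deliberate bound. The direction of the error stands. The bound is possible but undocumented: the only conservatism section 11.2 declares in its method is the Bonferroni adjustment.

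Unequal numbers of opened lesions also raise the design effect. Under the usual inflation, m(1 + CV²), an effective m of 20 needs CV² = 20/10 − 1 = 1.0 without a device (CV 1.0) and 20/7 − 1 = 1.86 with one (CV about 1.4). The protocol assumes neither. If opening itself had an ICC of 0.3 (an assumption, not a protocol figure), power for 65% at ICC 0.05 would be about 68%. That narrows the gap to 56% without closing it.

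A reader might infer four stronger things, none of which the protocol supports:
- *The dentin outcome is underpowered across the board.* The correction raises power at 65% to 75%.
- *The tables contradict the 20%-missing claim.* That sentence is expressly conditional on the observed difference and ICC. Power with 20% missing is still 91–97% at 70% and above 99% at 75%, so restricting the claim to the opening outcome would be wrong.
- *A 10-point difference is at best a coin toss.* That holds at the planning alpha of 0.025. At the planned per-comparison 0.05, power is 61% down to 48%.
- *A null result could not be interpreted.* Appendix E plans cluster-adjusted confidence intervals from the GEE models, and a null result would be read from those.

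**Conclusion.** The point holds as a minor, conservative error in stated power for a primary outcome, together with a mismatch between text and tables. The totals were reduced to opened lesions but the design effect was not. The size is zero at ICC 0 and up to about 18 points at 65% and ICC 0.05. At 70% and ICC 0.05 it is 11 points with 30 practitioners per group (95 against 84) and 13 with 27 (93 against 80).

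The announced 60% scenario is absent from both tables, so loss in reading the PDF is unlikely, though it cannot be fully excluded. On any of the bases computed, a 10-point difference has well under 80% power.

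These figures rest on the protocol's opening rates, its 50% dentin rate without a device, equal numbers of opened lesions per practitioner within an arm, and the planning alpha of 0.025 unless stated otherwise.

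**What to change.** In section 11.2, recompute both dentin tables with m = 10 (no device) and m = 7 (device), and state any allowance for unequal numbers of opened lesions. Alternatively, keep m = 20, declare it a conservative bound and give the reason. Add the 60% row to both tables, so that it is plain that a 10-point difference is not powered at 80%.

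Leave the 20%-missing sentence in section 11.3 and Appendix E applying to both outcomes. At most, add that for the dentin outcome adequate power with 20% missing holds for differences of about 20 points or more, and that at 15 points it is about 78% down to 66% at alpha 0.025 (86% down to 76% at alpha 0.05).

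The cost is two replaced tables and, at most, one added sentence in each of the two places. Sample size, design and analysis are unchanged.

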11.3 Final Analysis Plan

This is the planned analysis based on the data we plan to collect. An appropriate statistical model must take into account both the level of measurement of the outcome variables and the study design. Both of the primary outcome variables, surgical treatment of the lesion and extension into dentin, may be appropriately represented as dichotomous variables. Each practitioner will be randomized to use a single device, or no device and no a priori study design levels defined within the level of practitioner. This approach yields a two-level hierarchical study design. A characteristic of this two-level model is the presence of correlation among the multiple observations obtained from each practitioner. The primary analysis framework will be based on mixed-model logistic regression analysis, implemented with generalized estimating equations (GEE), accounting for correlation among the clusters of observations made by the same practitioners. These models will include a term representing the individual practitioner as a random effect and study arm as a fixed effect. Additional control variables, including region, may be included if it is found that these are needed to account for possibly different distributions of practitioner or patient characteristics. Details of the analysis approach and related considerations are provided in Appendix E

Initial exploratory analyses will be conducted for the entire study data set, in order to characterize the empirical distributions of each variable, to identify possible errors in the data, and to evaluate the proportion of missing values. Descriptive analyses will also be conducted to evaluate possible associations of practitioner and patient characteristics with outcome measures or other study variables. Depending on the specific structures of these auxiliary analyses, appropriate analysis models may include hierarchical methods, or single-level approaches such as contingency table analysis using the Chi-square statistic or ordinary analysis of variance or logistic regression analyses. Additional exploratory statistical analyses will be conducted to examine changes in practitioners' rates of operative treatment of lesions during the pre-randomization run-in period versus their rates during the post-randomization should be conducted to evaluate possible associations between pre- to post-randomization changes in practitioners' rates of operative treatment and variables representing practitioners' perception of changes in the decision-making process.

For evaluation of differences in proportions of lesions treated operatively among the intervention groups, the analysis data set will include all SOCLs that are enrolled by the study practitioners. The outcome variable for this analysis will be a dichotomous variable indicating whether the SOCL was treated operatively.

For the comparison of proportions of lesions treated operatively that have caries extending into dentin, the analysis data set will include all SOCLs that were treated operatively by the study practitioners. The outcome variable will be a dichotomous variable indicating whether the lesion extended into the dentin.

To determine whether the principal factors used by participating practitioners in managing SOCLs change when a caries detection device is employed, the Lens model analytic approach will allow for the determination of the unique contribution of each of the 4 principal features (color, luster, roughness, risk) to the treatment decision. An overall significance of each equation and the variance it accounted for will be determined for the decision to surgically intervene and the confidence of that decision. These represent the main a priori hypotheses from the decision study (vignette) portion of the project. In addition to those a priori hypothesized analyses, a number of more exploratory analyses are possible within the Lens model approach. This could include demographic characteristics of the dentists (age race, sex, experience in practice etc.). These individual difference variables would be included in the nomothetic analyses only. Finally, the similarity of treatment predictors will be examined across the in vivo and vignette portions of the study as an initial cross validation of the two approaches. We will examine the concordance rates and/or correlations between number of decisions to intervene across the two portions of the study and across groups (device trained vs. no device).

The proposed sample size, developed in the previous section was developed using conservative assumptions regarding effect size and potentially missing data. The study is anticipated to provide adequate statistical power even if approximately 20% of observations have missing values for some variables, depending on the differences and level of ICC that are actually observed in the study. Issues regarding missing values are presented in further detail in the Appendix E.

